We will recruit 60 healthy middle-aged people and randomly assign them to either daily intake of the NOVOS supplement (n=30) or placebo (n=30) for 6 months. The supplement (NOVOS) is a commercially available product and has 13 components. It was developed and is provided together with the placebo by AgeLess Sciences LLC, a Public Benefit Corporation. The study will require 2 visits by participants during which non-invasive vascular exams will be performed, venous blood taken and spot urine sample collected (Visit 1: 3 h, visit 2: 60 min). The primary endpoint is change in flow-mediated dilation, secondary endpoints are change in blood pressure, cholesterol, arterial stiffness, microvascular function cardiovascular risk SCORE and daily walking distance. Tertiary endpoints are changes in biomarkers of ageing as assessed in blood samples including DNA damage. In addition, we will assess anxiety, depressive feelings, happiness, well-being and the diet with several questionnaires. After consent, measurements will be taken on the first day before and 2 hours after ingestion of the first supplement or placebo. Participants will consume the supplement or placebo for 6 months and vascular exams and one blood draw will be repeated during the final visit. During the time, participants will receive 2 phone calls to improve compliance.

2. Background or rationale of the project

In our ageing society, extending the healthy lifespan is a major challenge and a healthy diet may play an import role in maintaining health throughout life. We know that with increasing age cardiovascular function declines and that large and small blood vessels change in various and complex ways and that these changes are also associated with the development of many age-related diseases. While vascular ageing is a key determinant of healthy ageing overall, a reason for the complexity of vascular ageing is that there are many molecular mechanisms involved. Animal and human studies suggest that dietary supplements may be able to affect these mechanisms.

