Secondary endpoints will be change in blood pressure and arterial stiffness as determined by an upper arm cuff and optical sensors and ECG. Additional secondary endpoints are carotid artery stiffness, intima-media thickness as assessed by carotid artery ultrasound and microvascular structure and function with optical coherence tomography angiography (OCTA) as assessed in parallel with FMD measurements on the arm. As additional secondary endpoints, we will assess blood biomarkers of cardiovascular health including blood lipids (fasting total cholesterol, fasting LDL, fasting HDL, ApoB, fasting triglycerides, and fasting insulin) and glucose control (fasting glucose and HbA1c). A change in cardiovascular risk score will be another secondary endpoint. We will used the Heart SCORE2 estimate 10-year risk of a myocardial infarction, stroke or cardiovascular death, based on age, sex, smoking habits, systolic blood pressure and non-HDL cholesterol (<https://www.escardio.org/Education/Practice-Tools/CVD-prevention-toolbox/HeartScore>). A pre-specified subgroup analysis will be performed in people with intermediate-high (<1% estimated 10-year cardiovascular risk) and high (>5% estimated 10 year cardiovascular risk) baseline CV risk. We expect more pronounced effects of the supplement in people with higher risk i.e. higher blood pressure or cholesterol at baseline. **Exploratory tertiary endpoints** will include blood biomarkers of inflammation (high sensitivity C-reactive protein, TNF-alpha receptor II, Interleukin 6), platelet reactivity, DNA damage (measured via γ H2AX in blood and 8-hydroxydeoxyguanosine in urine), ageing (growth differentiation factor 15, adiponectin, leptin), liver (transaminases) and kidney function (creatinine, cystatin C). We also want to explore novel biomarkers of aging, including epigenetic and transcriptomic aging clocks (on DNA samples), RNA and protein expression. In this regard, we will ask participants to allow us to store surplus blood, serum, plasma, RNA and DNA samples for future studies. To explore potential effects on dental health, we will take a digital photo of the teeth. Funding for the analyses needs to be obtained separately in the future. Sample processing and storage will comply with HTA regulations (see attached STAMINA_Human Tissue Governance Application Form V1.0.docx). Most blood and urine biomarkers will be analysed by Affinity Biomarker Lab. Governance including MTA is currently being prepared. The measurements (except for venous blood draws) will be entirely non-invasive, pain-free and require a single session of approximately 3 hours on the first day and 1 hour at 6 (3-6) months. Additional exploratory endpoints will be physical activity based on step/distance covered software on participants cell phone if they have this, dietary habits as assessed by food frequency questionnaire and 24 food recall and quality of life based on standard SQL questionnaire, and the completion at the start and end of the study of 8 questionnaires that assess anxiety, depressive feelings, happiness and well-being, given various substances in the formulation could also impact brain health and could contribute to improved cognitive and mental functioning, such as magnesium, glycine and Rhodiola rosea. All questionnaires are in the appendix. Pre-specified subgroup analyses will be performed in people with healthier diet, estimated high polyphenol intake at baseline and very high physical activity. These people may exhibit a smaller effect of the supplement.

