
Composition of supplement and placebo

The supplement mix is supplied as a powder to be mixed in water or other beverages like tea or coffee. The powder contains 12 ingredients, and it is commercially available (see also <https://novoslabs.com/>). All components are also part of a natural diet or are found naturally in the body. The supplement and matched placebo will be provided by AgeLess Sciences.

The composition is detailed in the table below. The placebo looks and tastes similar but does not contain the 12 supplements ingredients, only excipients and flavours.

Participants will receive a jar containing powder (supply of 6 months) with a spoon. Participants add one spoon of powder to 1 glass of water (240 ml), mix it and immediately drink it in the morning with breakfast. The participants will receive a paper diary to record at what time the supplement was consumed and if alone or with breakfast. If a dose is missed in the morning, they should just take it once they remember during the same day. If on a day the dose is missed entirely, we ask the participants to document this and carry on with the same amount on the next days but not take more than usual.

Table 1: Composition of one serving size (15 g) of supplement mix and placebo.

	VERUM Supplement mix	PLACEBO
Vitamin C (ascorbic acid)	100 mg	0
Magnesium (as magnesium malate)	304 mg	0
Calcium (as calcium alpha-ketoglutarate)	231 mg	0
Glycine	2,000 mg	0
Malate (as magnesium malate)	1,700 mg	0
Calcium alpha-ketoglutarate	1,100 mg	0
GreenGrown® glucosamine sulfate (vegan)	1,000 mg	0
Rhodiola rosea root extract (3% rosavins and 1% salidrosides)	300 mg	0
L-Theanine	150 mg	0
Hyaluronic acid	100 mg	0
Fisetin	100 mg	0
Organic ginger root extract (2% gingerols)	100 mg	0
Pterostilbene	50 mg	0
Lithium aspartate (providing 1 mg lithium)	20 mg	0
Other ingredients: Erythritol, malic acid, natural flavours, sodium bicarbonate, silicon dioxide, calcium silicate, stevia	X	X

“Overdosing” and adverse events

The recommended dose of the study supplement is 15 g which contains for example 100 mg Vit. C (approx. recommended daily intake 100 mg) and Lithium 1 mg (average daily intake). It is unlikely that participants will consume above the recommended dose as the supplement is insoluble in water if added in amounts above 15 g. However, to mitigate the unlikely occurrence of overconsumption, the following mitigation plan will be followed:

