- A diary will be completed to document the ingested amount every day and advise on not to take more than recommended.
- Training on preparing the solution will be conducted by the investigator staff on the first study day

Participants will be advised to call the investigator if they have consumed above the recommended dose or if any adverse event independent of dose occurs. The investigator will carefully assess any adverse events and advice accordingly and perform unblinding if required.

Sample size justification

The sample size is based on the primary endpoint FMD and the key secondary endpoints pulse wave velocity (PWV) and microvascular diameter.

Our previous experiments have shown average **FMD** values of 6% with standard deviation of 1%. While the supplement has not been tested in terms of effects on FMD, we expect a change in 1%. To detect this, we will need to study 17 verum subjects and 17 placebo subjects to be able to reject the null hypothesis that the population means of the verum and placebo groups are equal with probability (power) 0.8. The Type I error probability associated with this test of this null hypothesis is 0.05.

Our previous experiments have shown average **PWV** values of 9.3 m/s with the standard deviation of 1.3 m/s. While the supplement has not been tested in terms of effects on PWV, we expect a change in PWV of 1 m/s. To detect this, we will need to study 28 verum subjects and 28 placebo subjects to be able to reject the null hypothesis that the population means of the placebo and control groups are equal with probability (power) 0.8. The Type I error probability associated with this test of this null hypothesis is 0.05.

Our previous experiments have shown on average of **microvascular diameter using OCTA** of 48 μm with standard deviation is 6.4 μm . While the supplement has not been tested in terms of effects on microvascular diameter, we expect a change in diameter of 5 μm . To detect this, we will need to study 27 verum subjects and 27 placebo subjects to be able to reject the null hypothesis that the population means of the verum and placebo groups are equal with probability (power) 0.8. The Type I error probability associated with this test of this null hypothesis is 0.05.

Taken together, and taking 5-10% attrition into account we plan to recruit a total sample size of 60 (30 verum and 30 placebo).

Table 2: Schedule of events

Procedures	Visits (insert visit numbers as appropriate)

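### The only adverse-event route the protocol states is a call from the participant; no enquiry is stated for the scheduled calls or Visit 2, so mild events are likely to be under-reported

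*Protocol*

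**What the plan says.** The subsection on overdosing and adverse events in Protocol Section 9 states how events reach the investigator: "Participants will be advised to call the investigator if they have consumed above the recommended dose or if any adverse event independent of dose occurs". It then states what follows: "The investigator will carefully assess any adverse events and advice accordingly and perform unblinding if required". It mentions no routine enquiry, no form for recording events and no tabulation by arm.

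The scheduled contacts are described elsewhere. The study summary says that "participants will receive 2 phone calls to improve compliance" and that "vascular exams and one blood draw will be repeated during the final visit". Table 2 places the calls at months 2 and 4 and marks only questionnaires for them. For Visit 2 it marks questionnaires, the vascular exam, blood and urine. It has no adverse-event row.

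The daily diary is described twice, both times as an intake record: "The participants will receive a paper diary to record at what time the supplement was consumed and if alone or with breakfast" in the subsection on composition, and "A diary will be completed to document the ingested amount every day and advise on not to take more than recommended" under overdosing.

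**The concern.** When events come in only on the participant's initiative, what is recorded depends on how bothersome the event was and how willing the person is to telephone. Serious or alarming events will probably be reported. Mild ones may not be, and those are the kind the protocol itself foresees: the risk table in Section 10 names stomach upset, rated low in severity, as the outcome of taking too much product.

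The trial gives a multi-component product or placebo daily for a planned six months under double-blind conditions, and Section 2 says the effect of the combination on health parameters is unknown. It could therefore yield a blinded, placebo-controlled account of tolerability at almost no cost. If nobody asks, that account will be thin, and events never recorded cannot be recovered at analysis. For that reason the absence of a statistical analysis plan does not settle the point: such a plan governs how events are analysed, whereas whether they are elicited is fixed by the protocol and its schedule.

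**Working it through.** **Step 1. Each possible source of adverse-event data, checked in turn.**

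| Source | Where described | Stated content | Event enquiry stated? |
|---|---|---|---|
| Call from participant | Section 9, overdosing and adverse events | Overconsumption or any adverse event | Yes, if the participant calls |
| Month 2 and month 4 calls | Summary; Table 2 | Compliance; questionnaires | No |
| Visit 2 | Summary; Table 2 | Questionnaires, vascular exam, blood, urine | No |
| Diary | Section 9 | Time, amount, with or without breakfast, missed doses | No |
| Questionnaires | Summary; Section 9 | Mood, well-being, diet, quality of life | Not in the description; appendix not shown |
| Blood pressure and laboratory measures | Section 9 | Secondary or exploratory endpoints in both arms | Not symptoms, but systematic |

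One route is stated, and it is passive. The questionnaires leave some doubt. Section 9 describes "8 questionnaires that assess anxiety, depressive feelings, happiness and well-being" as completed at the start and end of the study, while Table 2 also marks questionnaires at months 2 and 4. What is asked in the calls is therefore not clear from the text.

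**Step 2. How far the scheduled contacts reach.** Section 9 allows follow-up of 3-6 months ± 1 month. Read literally, the earliest end is 3 − 1 = 2 months. A participant who finishes at about 3 months has no month 4 call, and one who finishes at 2 months may have Visit 2 at about the time of the month 2 call. Visit 2 is the one later contact that every completer has.

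**Step 3. Illustration of size.** The protocol gives 30 participants per arm. It gives no event risk p and no probability f that an affected person reports, so both are assumed here.

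Expected number recorded per arm = 30 × p × f. Chance of at least one = 1 − (1 − p × f)^30.

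| p | f | Expected recorded | Chance of at least one |
|---|---|---|---|
| 10% | 1 | 3.0 | 0.96 |
| 10% | 0.75 | 2.25 | 0.90 |
| 10% | 0.50 | 1.5 | 0.79 |
| 10% | 0.25 | 0.75 | 0.53 |
| 5% | 1 | 1.5 | 0.79 |
| 5% | 0.75 | 1.125 | 0.68 |
| 5% | 0.50 | 0.75 | 0.53 |
| 5% | 0.25 | 0.375 | 0.31 |

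For the comparison of arms, assume true risks of 30% and 10%, the same f in both arms, and a two-sided 5% test. Power = Φ((d − 1.96 × SE0) / SE1), where d is the difference in recorded risks, SE0 the pooled standard error and SE1 the unpooled one.

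- f = 1 (30% vs 10%): SE0 = √(2 × 0.2 × 0.8 / 30) = 0.1033 and SE1 = √((0.09 + 0.21) / 30) = 0.1000. Power = Φ((0.20 − 0.2024) / 0.1000) = 0.49.
- f = 0.5 (15% vs 5%): power about 0.25.
- f = 0.25 (7.5% vs 2.5%): power about 0.14.

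The normal approximation is rough at these counts; the direction matters more than the second decimal. No sample-size figure in the protocol is involved.

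**The case against.** The best reply has four parts.

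First, the calls are not shown to be silent on adverse events. Table 2 marks questionnaires at both, and their appendix is not shown. A reader might infer that nobody asks about adverse events at any scheduled contact. The documents support only that the text does not say anyone does. This stands, and the point is worded accordingly.

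Second, a reader might infer that the arms cannot be compared for tolerability. That does not follow. The trial is randomised and double-blind, and everyone gets the same advice, so under-reporting should be similar in both arms while the blind holds. The loss is in counts and sensitivity. Even full capture gives power of only about 0.49 in the illustration, so active questioning improves the comparison without making it strong.

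Third, some information on harm does not depend on who calls. Blood pressure, glucose control, transaminases and kidney markers are measured in both arms, and Sections 10 and 12 say how unexpected abnormal findings are handled. This also stands, though these measures do not capture symptoms.

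Fourth, the protocol lists no tolerability endpoint and promises no conclusion about tolerability. That limits the weight of the point. It does not remove it, because an account of harms will be expected from a six-month placebo-controlled trial whether or not it is an endpoint.

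**Conclusion.** The point holds as a modest, cheap improvement in data collection. Under-reporting of mild events is likely, on the general ground that volunteered reports miss what a direct question would find. Its extent is unknown: the figures above rest wholly on assumed risks and reporting rates, and a reader should not take any number of missed events as a finding about this trial. The conclusion also assumes that the unseen questionnaires match their description; if one of them contains an adverse-event item, the point shrinks to making that visible in Table 2. The primary endpoint, its analysis and the sample size are unaffected.

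**What to change.** Add an adverse-event row to Table 2. At each phone call that falls within the participant's own follow-up, and at Visit 2, blinded staff ask every participant the same open question about any health problem since the last contact. Record each event with onset and outcome, and tabulate by arm. Tying the question to calls within follow-up, with Visit 2 as the common last contact, accommodates those who finish before month 4. Keep the call-in route for events between contacts. If the appendix already holds such a question, refer to it in Section 9 and Table 2.

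The cost is about a minute per contact, at most 60 participants × 3 contacts = 180 minutes over the whole trial, plus one CRF page. No extra visit is needed. The one downside is a higher recorded count of minor events, many of which will have nothing to do with the product; the placebo arm gives the comparison needed to read them.

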- Subjects with or who have recently experienced traumatic injury, infections, or major surgery at the discretion of the qualified investigator.
- Subjects who are likely to start taking drugs/medication on a continuous basis or that will undergo surgery during the trial.
- Subjects engaged in donation or who were recipients of blood products within 90 days before the start of the study.
- Subjects with alcohol use of more than 2 alcoholic beverages per day within the past month.
- Subjects participated in a clinical trial with a medicinal, supplemental, nutraceutical or drug within the past two months prior to the first dose in the current study.
- If participants take fish oil supplements, they will be asked to stop taking these supplements 21 days before the start of trial and during the trial.
- Subjects using anti-inflammatory drugs on a chronic basis (e.g. aspirin, ibuprofen, diclofenac, celecoxib, etc).
- Subjects using supplements or substances present in formulation (malate, fisetin, glucosamine, alpha ketoglutaric acid, glycine, theanine, Rhodiola rosea, hyaluronic acid, ginger extract, pterostilbene, lithium). Participants will be asked to stop taking these supplements 21 days before the start of trial and during the trial.
- Subjects using supplements or substances similar as those used in the formulation (e.g. resveratrol (similar to pterostilbene) or quercetin (similar to fisetin)). Participants will be asked to stop taking these supplements 21 days before the start of trial and during the trial.
- Subjects taking NAD boosters, like NMN, nicotinamide riboside (NR), high-dose niacin (nicotinic acid), high-dose vitamin B3, high-dose nicotinamide (niacinamide) within 21 days before the start of the trial. Participants will be asked to stop taking these supplements 21 days before the start of trial and during the trial.
- Subjects with clinically significant abnormal laboratory results at screening.
- Known allergy/intolerance to any of the components in the supplement product.

Consent can be withdrawn at any time. In this case, all personal and research data will be deleted. After data have been anonymised, only personal data will be deleted and it will not be possible to delete research data after this point.

9. Experimental design, data collection and methods (including data analysis)

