In order to assess the vascular effects of the supplement mix, we will perform a 2 armed parallel group, randomised, controlled, double blind clinical trial. Healthy subjects will be recruited and after reviewing a participant information sheet and signing the informed consent document randomised to either the supplement or placebo and consume it daily over 6 months (3-6 months \pm 1 month to ensure completion of study and allow flexibility for participants). The randomisation will be based on a sequential list with equal numbers of treatments A and B, with one being placebo and one verum. Recruited participants

will also be numbered sequentially and receive the respective treatment (A or B). The containers of treatments will be labelled with either A or B. The identity of what was A and what was B will be stored in a sealed envelope in a locked cabinet in [name] office. The measurements will take place in the morning, after an overnight fast and in the fasting stage, before and at 2 hours after the first dose and once in the morning fasted at 6 months. After measurements are completed, participants will be offered a breakfast snack and drink. Venous blood samples (<50 ml) will only be taken once on each study day.

The **primary endpoint** will be a change endothelial function as assessed by flow-mediated dilation (FMD) with ultrasound on the brachial artery.

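### The stated 5-10% attrition allowance does not hold at 10% for pulse wave velocity: 60 recruited leaves 27 per arm against the 28 the protocol requires

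*Protocol*

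**What the plan says.** In Section 9 of the protocol, under the sample size justification, the size rests on three endpoints: the primary endpoint FMD and two key secondary endpoints, PWV and microvascular diameter by OCTA. Each is given a mean and SD from earlier experiments, an expected effect, and a number per arm for power 0.8. For each: "The Type I error probability associated with this test of this null hypothesis is 0.05".

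- FMD: SD 1%, effect 1%, 17 per arm.
- PWV: "values of 9.3 m/s with the standard deviation of 1.3 m/s"; then "we expect a change in PWV of 1 m/s. To detect this, we will need to study 28 verum subjects and 28 placebo subjects".
- Microvascular diameter: SD 6.4 µm, effect 5 µm, 27 per arm.

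The closing sentence combines the three: "taking 5-10% attrition into account we plan to recruit a total sample size of 60 (30 verum and 30 placebo".

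**The concern.** PWV has the largest requirement of the three, so it is the endpoint that an attrition allowance has to protect. Thirty per arm is only two above 28, and two in 30 is less than 10%. If the upper end of the attrition range occurs, the trial falls below the number that the same section says it needs for PWV. The recruitment total would then not do what the sentence says, on an endpoint that the size is expressly based on.

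**Working it through.** **Inputs** (protocol, sample size justification): alpha 0.05; power 0.8; effect and SD of 1 and 1 (FMD, %), 1 and 1.3 (PWV, m/s), 5 and 6.4 (diameter, µm); total 60, allocated 30 and 30; attrition 5-10%. Sidedness is not stated. I take it as two-sided, because the null is equality of means and a one-sided test would need only 13, 21 and 21 per arm (normal approximation), which are not the printed sizes.

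**Step 1. Reproduce the printed sizes.** Two-sample t-test with equal SDs: standardised effect d = effect/SD, noncentrality d × √(n/2), degrees of freedom 2n − 2. Solving for 80% power:

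| Endpoint | d | n per arm, exact | Rounded up | Printed |
|---|---|---|---|---|
| FMD | 1/1 = 1.000 | 16.7 | 17 | 17 |
| PWV | 1/1.3 = 0.769 | 27.5 | 28 | 28 |
| Diameter | 5/6.4 = 0.781 | 26.7 | 27 | 27 |

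All three match, so the method is not in doubt.

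**Step 2. Apply the stated attrition.**

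- 5%: 60 × 0.95 = 57, for example 28 and 29. The PWV requirement is met (power 81.4%).
- 10%: 60 × 0.90 = 54, or 27 per arm. This is one per arm below 28.
- Largest loss that keeps 56 in total: 1 − 56/60 = 6.7%, or four participants, if split evenly.

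Working forwards from the requirement gives the same answer. For PWV, 28/0.95 = 29.5, so 30 per arm covers 5%; 28/0.90 = 31.1, so 10% would need 32 per arm. For diameter, 27/0.90 = 30 exactly.

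**Step 3. Power with the printed SDs.**

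| n per arm | PWV | Diameter | FMD |
|---|---|---|---|
| 30 | 83.4% | 84.5% | 96.8% |
| 28 | 80.7% | 81.9% | 95.7% |
| 27 | 79.2% | 80.4% | 95.0% |

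For PWV at 27 per arm the noncentrality is 0.769 × √13.5 = 2.83 with 52 degrees of freedom. If the 54 are split unevenly, PWV power is 79.2% (26/28), 79.0% (25/29) or 78.7% (24/30).

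**Step 4. Optional: what baseline adjustment would give.** The protocol gives no baseline-to-follow-up correlation r, so r is an assumption shown as a range. For ANCOVA the residual SD is SD × √(1 − r²) with 2n − 3 degrees of freedom, and power is averaged over chance imbalance between the arms at baseline. PWV at 27 per arm:

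| r | 0 | 0.2 | 0.3 | 0.5 |
|---|---|---|---|---|
| Power | 78.4% | 80.0% | 82.1% | 88.7% |

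A simulation of 100,000 runs gave 78.6%, 80.1%, 82.0% and 88.8%.

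**The case against.** **The sentence can be read jointly.** It introduces the total as a summary over three endpoints. Thirty per arm covers PWV at 5% and diameter at 10%, so the range might be taken as spanning the endpoints. This does not rescue the claim. PWV is one of the three endpoints named as the basis of the size, it has the largest requirement, and nothing in the sentence limits the upper end of the range to the other two.

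**The normal approximation gives 80.7% at 27 per arm.** That is correct, but the same approximation yields 16, 27 and 26 per arm, not the printed 17, 28 and 27. By the method that the protocol evidently used, 27 is too few.

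**The gap is trivial.** This largely stands. It is 0.8 percentage points below 80% on a secondary endpoint, and the SDs and effects are planning values for a supplement not yet tested on these measures. It limits the weight of the point but does not make the sentence correct.

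**A reader might infer a larger fault from the wording of the endpoints.** The primary endpoint "will be a change endothelial function as assessed by flow-mediated dilation (FMD) with ultrasound on the brachial artery", and arterial stiffness is also worded as a change ("Secondary endpoints will be change in blood pressure and arterial stiffness as determined by an upper arm cuff and optical sensors and ECG"), while the printed SDs are those of measured values. It is tempting to conclude that the trial is too small. The protocol does not support that. Its null hypothesis is equality of the two group means, for which the SD of measured values is right if follow-up values are compared. Calling an endpoint a change does not fix an unadjusted change-score test; the choice of analysis can be left to a statistical analysis plan, which is not at hand. The SD of a change is SD × √(2(1 − r)), which exceeds the printed SD only if r is below 0.5, and r is not given. No loss of power is shown.

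**A reader might also tie attrition to the consent rule in Section 8**: "Consent can be withdrawn at any time. In this case, all personal and research data will be deleted". That rule covers withdrawal of consent before the data are anonymised. It does not cover a missed final visit or loss to follow-up, and it does not change the arithmetic above.

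**Conclusion.** The attrition statement is wrong as written at its own upper limit. It holds up to 6.7% loss; at 10% the PWV comparison has 27 per arm instead of 28 and 79.2% power instead of at least 80%. The conclusion rests on the printed effects and SDs, a two-sided t-test (inferred because it reproduces all three sizes) and an even split of losses; an uneven split down to 24/30 lowers the figure only to 78.7%.

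The point is minor. FMD needs 17 and keeps 95.0% power at 27 per arm, so nobody should infer that the primary endpoint is underpowered, and diameter keeps exactly its required 27. The shortfall does not by itself call for a larger trial.

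**What to change.** In the sample size justification, replace the attrition claim with wording such as:

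> 28 per arm is retained up to 6.7% attrition; at 10% (27 per arm) power is about 79% for PWV, 80% for microvascular diameter and 95% for FMD.

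This is a wording change only. No participants are added, and the cost is a less favourable statement. Enlarging the trial to cover 10% in full would mean 32 per arm (64 in total), which a gap of this size does not justify.

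Optional improvement: state that the groups are compared with adjustment for the pre-dose baseline value (ANCOVA), leaving the details of the model to the statistical analysis plan. The baselines are already collected at visit 1. PWV power at 27 per arm would then be about 78%, 80%, 82% and 89% at an assumed r of 0, 0.2, 0.3 and 0.5. The downside is just under one percentage point of power if r is 0 (78.4% against 79.2%).
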